## 6.8 Appendix 8: List of HRT and other drugs affecting bone mineral density

Manual review will be used to identify HRT and other drugs affecting bone mineral density based on the [Table 6–7](#) and [Table 6–8](#). Participants, who used any drugs affecting bone during the study will be excluded from the BMD analysis set. The list of the drugs affecting bone will be reviewed during the blind review of the data and finalized prior to unblinding.

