### Prior/Concomitant Therapy

13. Has used and is unwilling to wash-out use of any of the prohibited concomitant medications, as specified in Section 10.6.
14. Inability to comply with the use of prohibited medications as described in Sections 6.8.1 and 10.6

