**Table 9–2: Definition of the analysis sets.**

Analysis Set	Description
Enrolled	All participants who sign the informed consent form.
Full Analysis Set (FAS)	All randomized participants.
Safety Analysis Set (SAF)	All participants who receive at least one dose of study intervention.

Efficacy analyses will be based on the FAS and participants will be analyzed according to the randomized intervention. Safety analyses will be performed on the SAF and participants will be analyzed according to the intervention received.

Documentation of validity findings and assignment of participants to analysis sets will be performed according to the sponsor's applicable Standard Operating Procedures.

Details on additional subsets which may be of interest will be provided in the statistical analysis plan (SAP).

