#### **9.4.5 Other Safety Analysis**

All safety analyses will be descriptive and will be performed on the SAF. Safety data will be summarized descriptively for each treatment group.

All AEs will be coded using the latest version prior to data base lock of the Medical Dictionary for Regulatory Activities (MedDRA).

The percentage change from baseline in BMD in lumbar spine (total), total hip and femoral neck will be analyzed descriptively over time by treatment group in participants, who have BMD data available.

Further details on safety analyses will be described in the SAP.

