## 10.6 Appendix 6: Prohibited concomitant medications

**Table 10–4: Prohibited concomitant medication and conditions for selected allowed medication potentially confounding efficacy**

Prohibited from the time shown until 1 week after the last dose of study drug	
Hormonal therapies	
From 4 weeks prior to Baseline Visit	Vaginal hormonal products (rings, creams, gels and including DHEA or analogues thereof)
From 4 weeks prior to Baseline Visit	Transdermal estrogen alone or estrogen/progestin products
From 8 weeks prior to Baseline Visit	
 
• Oral estrogen and/or progestin therapy
 
• Selective estrogen receptor modulators
 
• Intrauterine progestin therapy
 

From 12 weeks prior to baseline Visit	
 
• Progestin implants and estrogen alone injectable drug therapy
 
• Use of adjuvant endocrine therapy (e.g. tamoxifen, aromatase inhibitors, GnRH analogues)
 

From 24 weeks prior to Baseline Visit	Estrogen pellet therapy or progestin injectable drug therapy
Non-hormonal therapies	
From 4 weeks prior to Baseline Visit	
Participants are permitted to continue to use antidepressant drugs and over the counter/herbal treatments (see details below) when the dose has been stable for at least 4 weeks and when it is anticipated to be stable for the duration of the study. In addition, the drug has been prescribed solely for the management of another disorder (e.g. neuropathic pain, depression).
 
Participants are not allowed to start with these drugs during the study:
 
 
• Anti-depressant drugs with effect on vasomotor symptoms (eg paroxetine, other including selective serotonin reuptake inhibitors, serotonin norepinephrine reuptake inhibitors and tri-cyclic antidepressants, alpha agonists [clonidine], methyldopa, gabapentin, pregabalin, medicinal cannabis or derivatives)
 
• Over the counter/herbal treatments including traditional Chinese medicine for treatment of menopausal symptoms.
 
• Oxybutynin/ Oxybutynin hydrochloride
 

DHEA = Dehydroepiandrosteronacetat, ICF = Informed consent form

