**Table 4–1: Definition of the analysis sets**

Analysis Set	Description
Enrolled	All participants who sign the informed consent form.
Full Analysis Set (FAS)	All randomized participants.
Safety Analysis Set (SAF)	All participants who receive at least one dose of study intervention.
BMD Analysis Set (BAS)	All randomized participants in sites assigned to perform DEXA, who have baseline and at least one post-baseline (week 24 and/or week 52) DEXA scan available and have not used HRT or some other drugs affecting bone density (other than vitamin D and calcium) until that time point

Efficacy analyses will be based on the FAS and participants will be analyzed according to the randomized intervention. Safety analyses will be performed on the SAF and participants will be analyzed according to the intervention received. The analysis of the Bone Mineral Density (BMD) will be based on the BAS and participants will be analyzed according to intervention received.

Documentation of validity findings and assignment of participants to analysis sets will be performed according to the sponsor's applicable Standard Operating Procedures.

Final decisions regarding the assignment of participants to analysis sets will be made during the review of study data and documented in the final list of important deviations, validity findings and assignment to analysis set(s).

Tables that are pre-specified to be displayed for FAS and SAF may be displayed for the FAS exclusively in case both analysis sets as well as the randomized intervention and the actual intervention received are identical.

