#### **5.6.3.8 Bone mineral density**

Bone mineral density (BMD) will be analyzed using BMD Analysis Set (BAS). List of HRT and other drugs affecting bone density will be given in the Section [6.8](#).

Summary statistics for the percentage change from baseline in BMD of lumbar spine, total hip and femoral neck (using the central reading results) will be provided by treatment group and visit.

The time course by visit and by treatment group will be shown using line plots depicting the mean  $\pm$  95% plot for the percentage change from baseline in BMD of lumbar spine, total hip and femoral neck.

Percentage change in BMD of lumbar spine, total hip and femoral neck from baseline with frequencies and percentages for the following categories:  $<-6\%$ ,  $\geq-6\% - <-3\%$ ,  $\geq-3\% - <-1.5\%$ ,  $\geq-1.5\% - \leq0\%$ ,  $>0\% - \leq1.5\%$ ,  $>1.5\% - \leq3\%$ ,  $>3\% - \leq6\%$  and  $>6\%$  will also be summarized by treatment group and visit.

The Z-score and the T-score and the respective change from baseline in Z-score and T-score by BMD location will be summarized by treatment group for each visit using descriptive statistics.

Z-score and T-score with frequencies and percentages for the following categories:  $\leq -2$  -  $\leq -1.5$  ,  $> -1.5$  -  $\leq -1$  ,  $> -1$  -  $\leq 0$  ,  $> 0$  -  $\leq 1$  ,  $> 1$  -  $\leq 1.5$  ,  $> 1.5$  -  $\leq 2$  and  $> 2$  will also be summarized by treatment group and visit.

Participants that had at least one DEXA scan with either BMD loss  $> 6\%$  from baseline to Week 24/Week 52 for any location or Z-score  $\leq -2$  SD for any location will be listed.

If the baseline scan at Screening Visit 2 is missing or not evaluable based on the evaluation from the imaging central laboratory, the participant is requested to have a repeat scan. If it's not possible to have this repeat scan performed before the start of treatment, this repeat scan is allowed to be performed shortly after the start of the treatment (within maximum of 15 days). Considering the BMD will not change quickly, this can be accepted from a medical point of view. If a BMD value performed after the treatment start date has been flagged as baseline, it will be analyzed as baseline.

Both scheduled and unscheduled measurements can be used in the analysis. The following time windows apply, when re-mapping measurements to the visits:

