- Week 24: Day 90 after Start of Treatment (SoT) to Day 239 after SoT , but no later than the date of last dose + 60 days
- Week 52: Day 270 after SoT to Day 419 after SoT, but no later than the date of last dose + 60 days

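### The SAP gives two different timing rules for removing users of bone-affecting drugs from the BMD Analysis Set, and plans no BMD summary in the protocol's wider population

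*SAP*

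**What the plan says.** SAP Table 4–1 defines the BAS as randomized women at DEXA sites who have a baseline scan and at least one scan at Week 24 or Week 52, and who "have not used HRT or some other drugs affecting bone density (other than vitamin D and calcium) until that time point". SAP Section 6.8 (Appendix 8), which lists the drugs, states: "Participants, who used any drugs affecting bone during the study will be excluded from the BMD analysis set".

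SAP Sections 4 and 5.6.3.8 base the BMD analysis on the BAS and name no other population. Section 5.6.3.8 also limits which scans count. For the later visit the window is: "Week 52: Day 270 after SoT to Day 419 after SoT, but no later than the date of last dose + 60 days".

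Protocol Section 9.4.5 describes the population without a drug condition. Percentage change in BMD "will be analyzed descriptively over time by treatment group in participants, who have BMD data available". The text under protocol Table 9–2 allows the SAP to add further subsets, so defining a BAS is legitimate in itself.

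**The concern.** The same analysis set has two definitions. One looks at drug use up to the scan, the other at drug use at any time in the study. Two programmers who each follow the SAP could build different sets. The BAS also supplies denominators for disposition (Section 5.2), exposure (5.6.1), demographics (6.6.1) and reproductive history (6.6.2), so those tables would differ too.

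The Appendix 8 version also lets a later, post-randomisation event decide whether an earlier scan counts. A drug first taken after a scan cannot have changed that scan. The later start may, however, be related to the scan result: protocol Section 8.2.8 leaves treatment decisions to the investigator on the local DEXA reading, and SAP Table 6–8 includes osteoporosis treatments. Many other listed drugs (HRT, SSRIs, glucocorticoids, heparins) would be started for reasons that need not involve bone.

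SAP Section 5.2 reports BAS counts by arm and reasons for exclusion, but nothing in the SAP shows what the exclusions do to the BMD result. Mean percentage change in BMD to Week 52 is a named safety endpoint, so its population should be unambiguous before unblinding.

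**Working it through.** No stated figure in the documents bears on this point, so the check starts with the text.

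**Membership by time of first on-study use.** Assume both scans were done and fall within their windows. Section 4 does not say whether a scan taken after drug use is dropped for a woman already in the set, so both readings are shown.

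| First use | Section 4, by visit | Section 4, by participant | Appendix 8 |
|---|---|---|---|
| None | Weeks 24 and 52 | Weeks 24 and 52 | Weeks 24 and 52 |
| Week 10 | Neither | Neither | Neither |
| Week 30 | Week 24 | Weeks 24 and 52 | Neither |
| Week 54 (follow-up) | Weeks 24 and 52 | Weeks 24 and 52 | Neither |

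The rules part exactly when first use follows a valid post-baseline scan. A woman on a listed drug throughout, such as a permitted stable SSRI, is out under both.

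**Whether such cases can arise.** Protocol Table 10–4 bans HRT and new VMS-active antidepressants for a limited time: "Prohibited from the time shown until 1 week after the last dose of study drug". Follow-up lasts 4 weeks, and women who stop treatment early are asked to stay until T9 (protocol Section 7.1). Oestrogens, progestogens and SSRIs are the drug groups in SAP Table 6–3 (alternative VMS treatment) and also appear in SAP Table 6–7 (drugs affecting bone). A woman who stops dosing after her Week 24 scan and then starts HRT meets the conflict without breaking the ban.

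**Limit from the scan window.** The earliest Week 52 scan is Day 270, so the last dose must be on or after Day 270 − 60 = Day 210. For a T9 scan on Day 351 it is Day 351 − 60 = Day 291. A woman who stopped earlier has no Week 52 value under any rule.

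**Illustration of size.** From the documents:
- BMD is planned in at least 50% of participants (protocol 8.2.8): 300 × 0.5 = 150 in the elinzanetant arm.
- 240 of 300 are expected to be treated for 6 months (protocol 9.2): 150 × 240/300 = 120 with a Week 24 scan.
- Expected untreated loss is 1–2% a year (protocol 8.2.8). Half of the 1.5% midpoint is 0.75% at Week 24.

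Assumed, because the documents give no rate: a share q first uses a listed drug after a valid Week 24 scan. Appendix 8 then removes 120 × q women whom Section 4 keeps: about 2 (q = 2%), 6 (5%), 12 (10%) or 24 (20%).

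The mean loss shown falls by q × (mean loss in those removed − 0.75). With q = 6/120 = 0.05:
- All six lost 0.75%: 0.05 × 0 = 0.
- One lost 3%, five lost 0.75%: mean (3 + 5 × 0.75)/6 = 1.125; shift 0.05 × 0.375 = 0.019.
- One lost 6%, five lost 0.75%: mean (6 + 5 × 0.75)/6 = 1.625; shift 0.05 × 0.875 = 0.044.
- All six lost nothing: 0.05 × (−0.75) = −0.0375.
- Extreme case, all six lost 3% or 6%: 0.1125 or 0.2625.

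These are percentage points in one arm's mean. The between-arm difference does not move if both arms shift alike.

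**The case against.** The best defence is that Section 4 governs. Table 4–1 is where analysis sets are defined. Section 5.6.3.8 sends the reader to Section 6.8 only for the drug list, and the SAP version history says Section 6.8 was added because that list was missing, with no change to the BAS recorded. On this view the Appendix 8 sentence is loose shorthand. Assignment to sets is also settled at blind review (Sections 4 and 6.6.3) and the drug list is fixed before unblinding, so the rule is unlikely to be chosen from unblinded results. Most of this stands, and Section 4 is probably the intended rule. But no text says so, blind review is not told which timing rule to apply, and a reviewer working from Appendix 8 would apply the other one.

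The pool of late starters is also limited. Besides HRT and VMS-active antidepressants, the protocol bans SERMs, GnRH analogues, cyclosporine, tacrolimus and several antiepileptics until 1 week after the last dose. During treatment the main routes left are glucocorticoids, heparins and osteoporosis drugs other than SERMs. This stands and supports a small expected effect.

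Excluding by participant is a defensible choice too, because it keeps later drug users out of both visits. It would still have to be stated once, and it keeps the dependence on future drug use.

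A reader might also infer that washed-out prior HRT users are shut out, since Section 4 gives no start date for non-use. Such women are eligible: exclusion criterion 13 reads "Has used and is unwilling to wash-out use of any of the prohibited concomitant medications". The inference needs Section 4 read alone. If Appendix 8 supplies the start (the study) and Section 4 the end (the scan), it falls away.

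**Conclusion.** The contradiction is certain from the text; its numerical consequence is not established. The two rules yield different sets for first on-study use after a valid post-baseline scan, and Appendix 8 as written discards scans the drug could not have affected. The SAP also narrows the protocol's BMD population to the BAS with no companion summary.

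BMD is descriptive and no hypothesis test depends on it. Size and direction are unknown and may be near zero. The 0.02 to 0.04 point illustration rests on an assumed 5% of late starters, of whom one in six had lost 3–6%.

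Three stronger readings are not supported. A reader might conclude that no BMD summary without the drug exclusion exists anywhere in the plan; protocol Section 9.4.5 describes one, so the gap is in the SAP only. A reader might place the effect mainly at Week 24; no use rates are given, and if Section 4 is read by participant, a start at Week 30 changes Week 52 as well. A reader might call the BMD comparison biased; nothing shows that late starters differ in bone loss or that the arms differ in late starts.

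**What to change.** 1. Replace the Appendix 8 sentence with the Section 4 rule, stated by visit in both places: at each visit, use scans taken before first on-study use of a listed drug. Count use from start of treatment, so that a drug ongoing on that date counts from Day 1 and washed-out prior use does not count. Leave the Section 5.6.3.8 visit windows and the 60-day limit after last dose unchanged. State that a participant belongs to the BAS, for the tables in Sections 5.2, 5.6.1, 6.6.1 and 6.6.2, if she has a baseline scan and at least one such post-baseline scan.

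2. Add a supporting summary of percentage change in BMD in all treated participants with a baseline and a post-baseline scan, regardless of listed drugs, in line with protocol Section 9.4.5.

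The cost is two wording edits and one repeated descriptive table set. No new scans or data are needed.

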**Table 6–7: List of HRT and other drugs affecting bone mineral density**

DGCODEL0	DGNAME0	DGCODEL1	DGNAME1	DGCODEL2	DGNAME2
		108	Drugs acting on gonadotropin-releasing hormone (GnRH) receptors	109	GnRH agonists
		108	Drugs acting on gonadotropin-releasing hormone (GnRH) receptors	110	GnRH antagonists
		99	Drugs used in diabetes	106	Thiazolidinediones
		5	Hormone replacement therapy	2	Oestrogens
		5	Hormone replacement therapy	3	Progestogens
274	Immunomodulators	186	Immunosuppressant drugs	418	Calcineurin inhibitors
126	Antithrombotic drugs	523	Heparins	524	Low molecular weight heparins (LMWH) and heparinoids
126	Antithrombotic drugs	523	Heparins	525	Other heparins
		772	Cancer therapies	738	Endocrine antineoplastic therapy
1633	Drugs for psychiatric disorders	111	Antidepressants	113	Selective serotonin reuptake inhibitors (SSRI)

**Table 6-8: List of HRT and other drugs affecting bone mineral density by drug code**

Drug group/class	Example	Drug Code	Reason	Comments
Bisphosphonates	alendronate risedronate zoledronic acid ibandronate	90049001001	treatment to Osteoporosis	ATC M05BA, Bisphosphonates
RANK ligand inhibitors	Denosumab(Prolia, or Xgeva)	90121401001	treatment to Osteoporosis	ATC M05BX, Other drugs affecting bone structure and mineralization and/or SDG subgroup Monoclonal antibodies - non antineoplastic
parathyroid hormone and parathyroid hormone-related protein analogs	Teriparatide abaloparatide	90089101001	treatment to Osteoporosis	ATC H05A Parathyroid hormones and analogues and/or SDG subgroup Other hormones and hormone modulators used as immunomodulators
Selective estrogen receptor modulators	raloxifene, bazedoxifene	90088001001	treatment to Osteoporosis	ATC G03XC SELECTIVE ESTROGEN RECEPTOR MODULATORS and/or SDG subgroup Oestrogens used in replacement therapy
Calcitonin	Calcitonin (Salmon)	90028101001	treatment to Osteoporosis	ATC H05BA Calcitonin preparations and/or SDG subgroup Other hormones and hormone modulators used as immunomodulators
Glucocorticoids	dexamethasone	90039201001	induce osteoporosis (side effect)	ATC H02AB,R03BA Glucocorticoids and/or SDG Corticosteroids
Antiepileptic drugs	phenytoin phenobarbital carbamazepine valproate	90035201001	induce osteoporosis (side effect)	ATC N03A Antiepileptics and/or SDG Anticonvulsants

